13.1.3 Summary of TEAEs by Preferred Term

In addition, TEAEs will be summarized by MedDRA PT. Each summary table will be presented by study period (i.e., Placebo-Controlled Treatment, and Open-Label Treatment) and treatment group as overall by treatment group. A subject experiencing multiple occurrences of an adverse event will be counted only once for each PT. The summaries will be presented for:

- TEAEs by PT
- Severe TEAEs by PT
- Study drug-related TEAEs by PT
- Severe Study drug-related TEAEs by PT
- AESIs by PT
- Serious TEAEs by PT
- Serious Study drug-related TEAEs by PT
- TEAEs leading to study drug discontinuation by PT
- TEAEs leading to death by PT

13.2 Clinical Laboratory Evaluation

[Table 17](#) shows clinical laboratory assessments (hematology, chemistry, lipid panel, thyroid panel, urinalysis, and other tests) will be performed. Laboratory parameters will be summarized

by treatment and post-baseline scheduled time point, based on actual treatment received at each scheduled time point.

Table 17 Clinical Laboratory Parameters

Chemistry	Hematology	Urinalysis	Thyroid
Glucose, fasting	Platelet count	Specific gravity	T3
Potassium	RBC count	pH	T4
Calcium	MCV	Glucose	TSH
Sodium	MCH	Protein	
BUN	% reticulocytes	Blood	
Creatinine	Hemoglobin	Ketones	Other
Total protein	Hematocrit	Bilirubin	LH
ALP	WBC count	Urobilinogen	FSH
ALT/SGPT	Neutrophils	Nitrite	SHBG
AST/SGOT	Lymphocytes	Microscopic examination	Renin
GGT	Monocytes		Aldosterone
Total bilirubin	Eosinophils		Male: Inhibin B
Direct bilirubin	Basophils	Lipid	Female: Estradiol
Total bile acids		Total cholesterol	Female: Prolactin
PT/INR		LDL	Female: Progesterone
PTT		HDL	Hy's Law
		Triglycerides	

Numeric results will be summarized using (8-point) descriptive statistics at baseline and at each scheduled post-baseline time point, unless otherwise specified. Changes from baseline at randomization will also be summarized by scheduled time point.

In addition, the number and percentage of subjects with potentially clinically significant abnormalities (PCSA, see [Table 18](#)) in selected chemistry and hematology parameters (i.e., above the specified upper limit or below the specified limit) will be summarized by scheduled time point.

The number and percentage of subjects who meet criteria for potential drug-induced liver injury as defined by Hy's law will also be summarized.

Table 18 Potentially Clinically Significant Abnormalities by Laboratory Parameter

Parameter	PCSA Low	PCSA High
Chemistry		
ALT		>3 x ULN
AST		>3 x ULN
ALP		>1.5 x ULN
Total Bilirubin		>1.5 x ULN
Total bile acids		> 10 $\mu\text{mol}/\text{L}$
Creatinine		> 1.8 mg/dL or > 0.4 mg/dL increase from baseline ($> 159.16 \mu\text{mol}/\text{L}$ or $> 35.37 \mu\text{mol}/\text{L}$ increase from baseline)
Sodium	< 130 mEq/L ($< 130 \text{ mmol}/\text{L}$)	>150 mEq/L ($> 150 \text{ mmol}/\text{L}$)
Glucose	< 3 mmol/L ($< 54 \text{ mg}/\text{dL}$)	
Potassium	< 3 mEq/L ($< 3 \text{ mmol}/\text{L}$)	$\geq 5.5 \text{ mEq}/\text{L}$ ($> 5.5 \text{ mmol}/\text{L}$)
Calcium		>11.4 mg/dL ($> 2.84 \text{ mmol}/\text{L}$)
BUN		> 30 mg/dL and > 10 mg/dL increase from baseline ($> 10.71 \text{ mmol}/\text{L}$ and $> 3.57 \text{ mmol}/\text{L}$)
INR		>1.5 x ULN
Total Bile Acids		>5 x ULN or >3 x ULN if ALT is >3 x ULN
FSH		>15 IU/L if baseline was <5 IU/L
Hematology		
Hemoglobin		$\leq 10 \text{ g}/\text{dL}$ and >2 g/dL reduction from baseline ($\leq 100 \text{ g}/\text{L}$ and $> 20 \text{ g}/\text{L}$)
Leukocytes		<500/ μL ($< 0.5 \times 10^9/\text{L}$)
Neutrophils		<1800/ μL and >500/ μL reduction from baseline
Platelets		<50,000/ μL ($< 50 \times 10^9/\text{L}$)

All laboratory results will be listed with reference ranges and range indicator (Low, High, or Clinically Significantly Abnormal). In addition, laboratory results that meet or exceed the pre-specified PCSA levels (Table 19) will be flagged.

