2.3.1.2 Testicular

Reversible testicular/spermatocyte degeneration/atrophy was consistently observed in chronic toxicity studies: in rats and dogs dosed with 2000 mg/kg/day (~79-fold [rat] and >200-fold [dog] higher exposure than the expected average exposure for the human dose in this study) for 13 weeks, in rats dosed with ≤1000 mg/kg/day (~39-fold higher) for 26 weeks, and in dogs dosed with 1000/500 mg/kg/day (>66-fold higher) for <20 weeks. Effects included smaller testes and/or epididymides, seminiferous tubule degeneration/atrophy, and germ cell debris and/or reduced sperm in epididymides. However, male reproductive studies in rats showed no impairment in fertility at the highest dose tested (1,000 mg/kg/day [~39-fold higher]). Additionally, no meaningful effects on clinical laboratory markers of testicular function (luteinizing hormone [LH], follicle-stimulating hormone [FSH], inhibin B, and sex hormone-binding globulin [SHBG]) have been observed in male subjects in the Phase 1 or Phase 2 clinical studies.

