2.3.3 Assessment of Potential Risks and Benefits

Multiple study design elements have been incorporated to mitigate the potential risks of LFT laboratory abnormalities, testicular injury, and thyroid effects described in [Section 2.3.1](#). First, these risks are all associated with higher doses of tildacerfont; in this study, tildacerfont tablets will be administered at a total daily dose of 200 mg, lower than the doses at which elevated LFTs have been observed and doses that have been well tolerated. Additionally, clinical laboratory measures of liver chemistry, testicular function, and thyroid function will be assessed at every study visit in this study. Liver chemistry will be monitored by measuring ALT, AST, alkaline phosphatase (ALP), GGT, total and direct bilirubin, total bile acids, prothrombin time (PT)/international normalized ratio (INR), and partial thromboplastin time (PTT). Testicular function will be monitored by measuring LH, FSH, inhibin B, and SHBG and performing scrotal ultrasounds. Thyroid function will be monitored via a thyroid panel that measures T3, T4, and TSH. Finally, strict individual treatment-stopping criteria for liver chemistry findings and criteria for increased liver chemistry monitoring are in place (see [Section 7.1.1](#) and [Section 13.2](#)).

The reversible histopathological effects of tildacerfont on the male reproductive tract in rat and dog toxicity studies occurred in the context of animals with normal, rather than elevated, baseline hormone function. As a CRF₁ receptor antagonist, tildacerfont is intended to reduce abnormally elevated ACTH and androgen levels. In healthy animal models where baseline hormone levels are within normal ranges, clinical benefits are not expected, and indeed, effects on male reproductive tissues may be expected as a result of androgen reduction outside of the normal range. However, in patients with CAH, whose baseline ACTH and androgen levels are pathologically elevated, androgen reduction would be considered a positive, therapeutic effect.

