5.2.5.2 Contraception Guidelines for Female Subjects

A female enrolling in this study must meet ONE of the following contraceptive criteria from Screening until 30 days after the last dose of study drug:

1. Is postmenopausal at Screening

A postmenopausal state is defined as no menses for at least 1 year without an alternative medical cause. A high FSH level in the postmenopausal range may be used to confirm a postmenopausal state in women not using hormonal contraception or hormonal replacement therapy. However, a single FSH measurement is insufficient to establish a postmenopausal state without at least 1 year of amenorrhea.

2. Has documentation of one of the following performed before Screening:

- a. Hysterectomy
- b. Bilateral salpingectomy
- c. Bilateral oophorectomy

3. Is sexually abstinent from penile-vaginal intercourse as her usual and preferred lifestyle (abstinent on a long-term and persistent basis) and agrees to remain abstinent from Screening until 30 days after the last dose of study drug

4. Any male sexual partner is vasectomized, and the absence of sperm has been confirmed

5. Agrees to use one of the following highly effective contraceptive methods, which must be in place from at least 1 month before Screening until 30 days after the last dose of study drug:

- a. Combined hormonal contraception (containing estrogen and progestogen) associated with inhibition of ovulation: oral, intravaginal, or transdermal

Any hormonal contraception containing ethinyl estradiol must contain ≤ 35 μ g ethinyl estradiol, is permitted only for subjects who would not be considered at high risk for thromboembolic or cardiovascular complications with estrogen use, and must be used simultaneously with a backup method of contraception. Acceptable backup methods of contraception include diaphragm with spermicide, cervical cap with spermicide, vaginal sponge with spermicide, and male or female condom with or without spermicide. Dosing of oral formulations of hormonal contraception containing ethinyl estradiol should be offset by approximately 10 hours from the evening dose of study drug. The Investigator may consult with the Medical Monitor regarding such individuals.

- b. Progestogen-only hormonal contraception associated with inhibition of ovulation:
oral, injectable, or implantable

- c. IUD
- d. IUS
- e. Bilateral tubal occlusion

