9.4.7.3 Adverse Event Data

AEs will be coded using the Medical Dictionary for Regulatory Activities (MedDRA). AE summaries will be presented by System Organ Class, Preferred Term, severity, and frequency and percentage of subjects reporting each observed event.

AEs that occur before the first dose of study drug will be distinguished from TEAEs (defined in [Section 8.3.1](#)). All AEs and TEAEs will be listed by subject. The frequency of subjects who experience TEAEs will be summarized overall and by treatment group. TEAEs will also be summarized by relationship to study drug and severity.

Listings will be provided for subjects who experienced an SAE or discontinued study drug/withdrew from the study because of an AE.

9.4.7.4 *Laboratory Data*

Clinical laboratory test results will be listed by subject. Reference ranges provided by the laboratory for each parameter will be used to evaluate the clinical significance of laboratory test results. Values outside the relevant reference range will be flagged in the listings. Abnormal clinical laboratory test results will be listed in a separate listing.

Laboratory data will be summarized in terms of observed values, changes from baseline, values relative to normal ranges, and changes from baseline relative to normal ranges. Subjects meeting specific thresholds for laboratory data will also be summarized as specified in the SAP.

P-values for change from baseline and change from placebo or differences in proportions meeting specific thresholds will be derived using the appropriate statistical test as specified in the SAP.

Additional subgroup analyses based on baseline laboratory data [elevated, normal] will be specified in the SAP.

9.4.7.5 *Vital Signs Data*

Vital signs data will be summarized within appropriately defined categories in terms of observed values (by time point), changes from baseline (by time point), and counts and percentages. Subjects meeting specific thresholds for vital sign data will also be summarized as specified in the SAP.

P-values for change from baseline and change from placebo will be derived using t-tests as specified in the SAP.

9.4.7.6 *ECG Data*

The QTcF, PR interval, QT interval, QRS duration, and heart rate from standard digital ECGs will be summarized within appropriately defined categories in terms of observed values, changes from baseline, and counts and percentages.

9.4.7.7 *Psychiatric Evaluations*

C-SSRS and HADS data will be listed.

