9.7 Examination of Subgroups

Subjects will be categorized into the following common subgroups for the purposes of evaluating the Primary and Secondary Efficacy Endpoints.

- Sex (Male, Female)
- Baseline GC dose in HCe
 - < 40 mg/day, \geq 40 mg/day
 - < 35 mg/day (For endpoint 2.2 and 3.7 only)
- Baseline A4 levels (A4 \leq ULN, A4 $>$ ULN)

In addition, all potential subgroup x subgroup combinations are also pre-specified. If the primary analysis is positive, exploratory subgroup analysis for age, race, ethnicity, and region will be used to further evaluate the Primary and Secondary Efficacy endpoints.

Comparisons will only be provided for subgroups where each subgroup has at least 10 subjects. Additional subgroups specific to only select endpoints are specified in the appropriate section in the SAP.

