13 SAFETY ANALYSES

Safety will be evaluated by AEs, SAEs, AESIs, clinical laboratory, vital, ECG findings, monitoring for suicide risk and depression/anxiety, as well as physical examination. All analyses of safety data will be performed using the safety analysis set, based on the actual treatment a subject received. All descriptive statistics will be presented by treatment group and treatment period.

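### LH, FSH, SHBG and the FSH flag are summarised with men and women together, although the Protocol relies on them to monitor a testicular risk

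*SAP*

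**What the plan says.** SAP 13 sets the general layout for safety outputs: "All descriptive statistics will be presented by treatment group and treatment period". SAP 13.2 then has laboratory parameters summarised "by treatment and post-baseline scheduled time point, based on actual treatment received at each scheduled time point". Neither mentions sex. Table 17 marks inhibin B as male and estradiol, prolactin and progesterone as female; LH, FSH and SHBG carry no such mark. The FSH flag in Table 18 is a single rule for all subjects: ">15 IU/L if baseline was <5 IU/L".

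The Protocol gives these hormones a specific role. Section 2.3.3 states: "Testicular function will be monitored by measuring LH, FSH, inhibin B, and SHBG and performing scrotal ultrasounds". Section 2.3.1.2 describes the animal testicular findings and notes that no meaningful effects on these markers "have been observed in male subjects in the Phase 1 or Phase 2 clinical studies".

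No planned subgroup adds a split by sex. The sex subgroup in SAP 9.7 is defined "for the purposes of evaluating the Primary and Secondary Efficacy Endpoints". Protocol 9.4.7.4 promises a laboratory subgroup of another kind: "Additional subgroup analyses based on baseline laboratory data [elevated, normal] will be specified in the SAP".

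**The concern.** The question behind these markers is about men, and the summary as written answers it for men and women together. Of the four blood markers named in Protocol 2.3.3, only inhibin B gets a male summary. Ultrasound does not fill the gap, because after baseline it is repeated only in men who had a TART at baseline (Protocol 1.3.4, footnote 13).

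The female rows also carry a different signal. Postmenopausal women may enrol, and Protocol 5.2.5.2 says: "A high FSH level in the postmenopausal range may be used to confirm a postmenopausal state". Observed FSH values therefore mix populations with different expected levels.

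At stake is how readily a reader of the summary tables can see, or rule out, a drug effect on testicular function. The pooled mean shrinks a male-only shift, and the flag count does not say how many flagged subjects are men.

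There is a smaller issue with the flag percentage. Only subjects with baseline FSH below 5 IU/L can ever be flagged, yet SAP 8.1 reduces denominators only for missing values. On a literal reading, subjects who cannot be flagged stay in the denominator.

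**Working it through.** The plan states no figure on this point, so there is none to reproduce. The calculations below only illustrate the effect of pooling.

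**Inputs**
- From the documents: 45 subjects per arm (Protocol 9.2) and the flag rule (SAP Table 18).
- Assumed, because the documents do not give them: male share p = 0.3, 0.4, 0.5 or 0.6 (about 14, 18, 22 or 27 men per arm); a mean FSH shift of +3 IU/L in men; a shift d in women; standard deviations of change; four flagged men and no flagged women; the fraction with baseline FSH below 5 IU/L.

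**Mean change.** Pooled shift = 3p + d(1 − p).

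| Shift in women, d (IU/L) | p = 0.3 | p = 0.4 | p = 0.5 | p = 0.6 |
|---|---|---|---|---|
| 0 | 0.9 | 1.2 | 1.5 | 1.8 |
| −1 | 0.2 | 0.6 | 1.0 | 1.4 |
| +1 | 1.6 | 1.8 | 2.0 | 2.2 |

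**Median change.** With normal changes and d = 0, the pooled median x solves p·Φ((x − 3)/s_m) + (1 − p)·Φ(x/s_f) = 0.5, where s_m and s_f are the SDs in men and women. With both SDs equal to 2, x = 0.80, 1.14, 1.50 and 1.86 for the four values of p. Over s_m = 2 or 4 and s_f = 2, 4 or 8, x runs from 0.51 (p = 0.3, s_m = 4, s_f = 2) to 2.57 (p = 0.6, s_m = 2, s_f = 8). That is 17% to 86% of the male shift, so the median can be diluted more or less than the mean.

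**Flag percentage, four flagged men in one arm**

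| Denominator | p = 0.3 | p = 0.4 | p = 0.5 | p = 0.6 |
|---|---|---|---|---|
| All 45 subjects | 4/45 = 8.9% | 8.9% | 8.9% | 8.9% |
| Men with baseline <5, if all men qualify | 4/14 = 28.6% | 4/18 = 22.2% | 4/22 = 18.2% | 4/27 = 14.8% |
| Men with baseline <5, if half qualify | 4/7 = 57.1% | 4/9 = 44.4% | 4/11 = 36.4% | 4/14 = 28.6% |
| Both sexes with baseline <5, if half of each qualify | 4/23 = 17.4% | 17.4% | 17.4% | 17.4% |
| Both sexes with baseline <5, if all men and a quarter of women qualify | 4/22 = 18.2% | 4/25 = 16.0% | 4/28 = 14.3% | 4/31 = 12.9% |

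The first row differs from the second and third in two ways, denominator and sex. The effect of the sex split alone is seen on a matched at-risk denominator: 57.1 to 28.6% against 17.4% if half of each sex qualify, but 14.8% against 12.9% at p = 0.6 if all men and a quarter of women qualify. The dilution can therefore be small.

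**The case against.** The strongest reply is that pooling is inferred from silence. The SAP nowhere says that the sexes are combined, and SAP 8 assigns presentation conventions to the Appendix A mock-shells, which were not available. Those shells could already split by sex. This stands as a limit: the point is about what the SAP text specifies.

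Other mitigations also stand:
- Randomisation is stratified by sex, so pooling should dilute the comparison between arms but not confound it.
- Change from baseline is summarised, which removes stable differences in level. The baseline condition keeps women with a high postmenopausal baseline out of the flag numerator. The menopause argument therefore bears mainly on observed values.
- Inhibin B is male-only, all results are listed and flagged, investigators assess reproductive hormone changes under Protocol 7.1.6, and the DSMB sees unblinded safety data.
- The animal findings were reversible and arose at roughly 39-fold to more than 200-fold the expected exposure, with no impairment of fertility in male rats.
- No passage defines the denominator for the Table 18 percentages. The denominator point is a literal reading of SAP 8.1, and an all-subjects denominator could be defended.
- A split makes cells small. With seven men at risk, one man is 1/7 = 14.3 percentage points, and seven is below the 10-subject minimum that SAP 9.7 sets for its subgroup comparisons.

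These points keep the severity low. None of them supplies a summary of LH, FSH or SHBG in men by arm; a reader would have to rebuild one from the listings.

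**Conclusion.** The concern holds as a low-severity improvement to the SAP text. Read literally, SAP 13 and 13.2 combine men and women on three markers, and on a flag, that the Protocol uses to watch for a testicular effect. If women do not shift, a male-only mean shift appears at the male fraction of its size (30 to 60% under the assumed sex mix). The loss for the median and the flag ranges from slight to large, depending on spreads and baseline FSH values that the documents do not give. The outputs are descriptive, and no hypothesis test, estimand or stopping rule is affected. If the mock-shells already split these rows by sex, all that remains is to say so in the SAP.

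**What to change.** Add two sentences to SAP 13.2. The first: LH, FSH and SHBG (observed value and change from baseline) and the Table 18 FSH flag are presented separately for men and women, by treatment and visit. The second: the flag percentage is based on subjects of that sex with baseline FSH below 5 IU/L. The by-sex display is the essential part; the denominator rule matters less.

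Read the male rows together with inhibin B as the testicular safety output. Keep the female rows, because Protocol 7.1.6 also covers reproductive hormone changes in women.

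The cost is a few more tables with smaller cells: about 14 to 27 men per arm under the assumed split, and 7 to 27 in the flag denominator if 50 to 100% of men start below 5 IU/L. No new data are needed, since sex is a randomisation stratum. The SAP already uses sex-specific QTcF limits in Table 20, so separating the sexes in a safety output has precedent. Making the change before database lock keeps the male display prespecified.

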7.4 Safety Analysis Set

The Safety (SAF) Analysis Set is defined as all subjects who received at least one dose of study drug (placebo or tildacerfont). The safety analysis set, which will be based on the actual treatment received, will be used for evaluation of general medical history, study drug exposure, concomitant medication, and safety. Placebo-treated subjects who received any amount of tildacerfont during the Open-Label Period will be assigned to the tildacerfont treatment group from the time when tildacerfont was received.

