8.3.4 Tildacerfont Treatment Day

Tildacerfont Treatment Day 1 is defined as the first dose date of tildacerfont in the study, following the same format as study day. For subjects randomized into the tildacerfont treatment group in the Placebo-Controlled Treatment Period, the first dose date of tildacerfont is defined as the first double-blinded dose date in the Placebo-Controlled Treatment period. For subjects

randomized into the placebo treatment group in the Placebo-Controlled Treatment Period, the first dose date of tildacerfont is defined as the first dose date in the Open-Label Period. Tildacerfont Treatment Day will be included in select efficacy listings.

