8.3.9 Baseline Values

8.3.9.1 Baseline at Randomization

Baseline at randomization values are defined as the last non-missing assessment prior to the first dose of randomized, double-blind study drug in Placebo-Controlled Treatment Period of the study. Baseline at randomization will be used in the Primary Efficacy Endpoint, Secondary Efficacy Endpoint, and exploratory endpoint analyses that explore treatment at Week 24. Demographics and summaries of change from baseline will use baseline at randomization unless otherwise specified.

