8.3.9.2 Baseline Prior to Treatment with Tildacerfont

Baseline values prior to treatment with tildacerfont are defined as the last non-missing assessment prior to the first dose of tildacerfont. For subjects randomized into the tildacerfont treatment group of the Placebo-Controlled Treatment Period, the first dose of tildacerfont is defined as the first double-blinded dose date in the Placebo-Controlled Treatment period. For subjects randomized into the placebo treatment group of the Placebo-Controlled Treatment Period, the first dose of tildacerfont is defined as the first dose in the Open-Label Period. The baseline prior to treatment with tildacerfont will be used in Secondary Efficacy and Exploratory Efficacy Endpoint analyses that explore effects after 52 weeks of tildacerfont treatment.

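### Open-label safety changes for subjects who switch from placebo are reported as tildacerfont but measured from the randomisation baseline, so they include 24 weeks on placebo

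*SAP*

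**What the plan says.** Five places in the SAP combine to set the rule.

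- **Reference value, laboratory data (13.2).** "Changes from baseline at randomization will also be summarized by scheduled time point". This is explicit and has no exception for the open-label period.
- **Treatment label, laboratory data (13.2).** Summaries are "based on actual treatment received at each scheduled time point".
- **Subjects who switch (7.4).** "Placebo-treated subjects who received any amount of tildacerfont during the Open-Label Period will be assigned to the tildacerfont treatment group", counted from the time they receive it. Table 10 gives the whole open-label period a single label, tildacerfont 200 mg QD.
- **What the baseline is (8.3.9.1).** "Baseline at randomization values are defined as the last non-missing assessment prior to the first dose of randomized, double-blind study drug". For a placebo subject this value precedes the 24 placebo weeks. It is also the general default: "Demographics and summaries of change from baseline will use baseline at randomization unless otherwise specified". Sections 13.3 (vital signs), 13.4 (ECG) and 13.6.1 (HADS) name no other baseline, so they inherit it.
- **The alternative (8.3.9.2).** The SAP defines a second baseline, the last value before the first tildacerfont dose, and says where it applies: "The baseline prior to treatment with tildacerfont will be used in Secondary Efficacy and Exploratory Efficacy Endpoint analyses" that look at effects after 52 weeks on drug. Safety is not named. The on-drug clock is likewise assigned to efficacy output: "Tildacerfont Treatment Day will be included in select efficacy listings".

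Protocol 9.4.6 leaves the baseline for each evaluation period to the SAP. One of its listed periods compares the placebo group's Week 52 with that group's own Week 24.

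**The concern.** At the switch the SAP changes the treatment label but not the reference value. For a subject randomised to tildacerfont, the Day 1 value is the last one before drug. For a switcher, it is the last one before 24 weeks of placebo. Both kinds of subject then fall under the tildacerfont label, so one column holds changes with two different meanings.

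The placebo weeks cannot be assumed neutral. The A4-based algorithm adjusts glucocorticoid dose in both arms from early in the placebo-controlled period, so laboratory values or vital signs could move before any tildacerfont is taken. A shift that arose on placebo would be shown as change on drug, and a change on drug that reversed a placebo-period shift would be partly cancelled. The SAP avoids this mismatch in its analyses of efficacy after 52 weeks on drug and leaves it in place for safety.

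**Working it through.** **Step 1. The split.** Inputs from SAP 6: difference 7.25 mg/day, SD 10.5 mg/day, two-sided alpha 0.05, power 90%.

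n per group = 2 × (1.960 + 1.282)² × 10.5² / 7.25² = 2 × 10.51 × 110.25 / 52.56 ≈ 44.1, rounded up to 45. The plan's figure is reproduced (power at 45 per group is 0.906 by the normal formula). It matters here only as the source of the 45:45 split under 1:1 randomisation.

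**Step 2. Share of the column.** Let rP and rT be the fractions of the placebo and tildacerfont arms that enter the open-label period. The switchers' share is w = 45 rP / (45 rP + 45 rT).

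- Equal retention: w = 45/90 = 50%.
- rP = 0.8, rT = 1.0: w = 36/81 = 44%.
- rP = 1.0, rT = 0.8: w = 45/81 = 56%.

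The 80% to 100% range is an assumption, because the documents give no dropout rate.

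**Step 3. What is carried in.** For a switcher at week t,

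Y(t) − Y(0) = [Y(t) − Y(24)] + [Y(24) − Y(0)],

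where only the first bracket is change on tildacerfont. Let d be the mean of the second bracket among switchers. The pooled column mean then contains w × d that is not change on drug: 0.50d with equal retention and 0.44d to 0.56d over the assumed range. With the 8.3.9.2 baseline the second bracket disappears and the carried-in amount is 0.

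**Step 4. How much of the interval is placebo.** For a switcher, 24 of the t weeks are on placebo.

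| Visit | Weeks on drug | Placebo share of interval |
|---|---|---|
| Week 32 | 8 | 75% |
| Week 40 | 16 | 60% |
| Week 52 | 28 | 46% |
| Week 64 | 40 | 38% |
| Week 76 | 52 | 32% |

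Laboratory tests and vital signs are scheduled at all five visits, ECG and HADS at Weeks 52 and 76 only. Week 24 is not clearly affected, because open-label dosing starts the day after.

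**Step 5. Which flags depend on a baseline.**

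- Table 18: creatinine (rise above 0.4 mg/dL, sufficient alone), BUN, haemoglobin and neutrophils (each also needs an absolute abnormality), and FSH (above 15 IU/L with a baseline below 5 IU/L).
- Table 20: heart-rate change and QTcF change.
- Not baseline-relative: ALT, AST, ALP, bilirubin, bile acids and INR, which use fixed limits or multiples of ULN. Hy's law is summarised separately. There is no thyroid flag.

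**The case against.** The strongest reply is that little of consequence depends on this. The safety endpoint is AEs and SAEs, which are not changes from a measured baseline. The liver flags are absolute and the randomised 24-week comparison is intact. Laboratory and ECG values are summarised at each scheduled time point alongside the changes, so the Week 24 placebo column shows the group-level placebo shift. Results are also listed by subject, so change from Week 24 can be recovered. All of that stands, and it limits the scope of the point. It does not make the change tables themselves correct.

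A second reply is that SAP Section 13 presents results by treatment group and period, and that the mock shells in Appendix A may split columns by sequence. The shells were not available, so the final layout cannot be confirmed. Separation by period does not help, because both arms carry the tildacerfont label within the open-label period. A split by sequence would show where the placebo part sits, but the switchers' change and flags would still be counted from Day 1.

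A third reply is that change from randomisation is a legitimate quantity: Protocol 9.4.6 lists baseline to Week 76 as an evaluation period for select endpoints. That is fair. The randomisation baseline is not wrong in itself. It is wrong as the reference for a change labelled as on tildacerfont in a switcher.

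A reader might infer more than the documents support:

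- **That a liver or thyroid signal will be created or hidden.** Those organs are touched only through descriptive mean changes.
- **That flag rates among switchers will be inflated by a known amount.** This needs within-subject variability, which the documents do not give. If values simply drift with time, subjects randomised to tildacerfont would be flagged just as often over the same interval.
- **That the 30% placebo response in the sizing shows a large shift.** It describes a glucocorticoid reduction with A4 at or below ULN and gives no size for any laboratory, ECG or vital-sign change.

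**Conclusion.** The point holds for descriptive open-label safety changes and for the seven baseline-relative flags: creatinine, BUN, FSH, haemoglobin, neutrophils, heart-rate change and QTcF change. It is explicit for laboratory data. For ECG, vital signs and HADS it follows from the 8.3.9.1 default.

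The bias in a pooled mean change is w × d, about d/2, and can go in either direction. It rests on the 1:1 split, on retention similar enough to keep w near one half, and on both arms being pooled under one tildacerfont label as the SAP text implies. Because d is unknown, no material bias is demonstrated. What is shown is that the tables as specified cannot separate placebo-period change from change on drug. This should be corrected before the open-label tables are produced, but it does not threaten the primary analysis or the controlled safety comparison.

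**What to change.** In SAP 8.3.9.2, 13.2, 13.3, 13.4 and 13.6.1:

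1. State that on-tildacerfont open-label safety changes, and the baseline-relative flags in Tables 18 and 20, use the baseline prior to tildacerfont. This is the Day 1 value for the tildacerfont arm and the last value before the first open-label dose for the placebo arm.
2. Show open-label columns by randomised sequence (tildacerfont to tildacerfont, placebo to tildacerfont). This also separates unequal exposure: at Week 32, one group has had 32 weeks on drug and the other 8.
3. Keep the randomisation baseline for the placebo-controlled period and for any baseline-to-Week 76 summary, labelled as such.

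The cost is SAP wording, an extra column in the open-label safety tables and a footnote distinguishing the two baselines. The protocol already schedules laboratory, vital-sign, ECG and HADS assessments at Week 24, and the SAP already defines the baseline, so no new data or design change is needed.
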